6.9.2 Timing

Adverse events will be collected from the time of the signing of the Informed Consent/Assent until resolution or 30 days after the last dose or early termination, whichever comes first. At each specified timepoint, the patient (or parent/legal guardian) will be asked to report any and all AEs experienced since the previous assessment or visit. Specifically, the patient (or parent(s)/legal guardian(s) if the patient is a child), will be asked if the patient experienced any signs and symptoms that may indicate a thromboembolic event occurred. These may include, among others, headache, shortness of breath, chest pain, cyanosis, calf pain, swelling/edema, or redness.

If an AE occurs in PERSEPT 3 and the patient is still enrolled in PERSEPT 2, the AE should only be collected in PERSEPT 3. If the AE is ongoing at the time of rejoining PERSEPT 2, that AE should be only collected in PERSEPT 2 under medical history. If when rejoining PERSEPT

2, there is an exacerbation or recurrence of the AE, this AE should be collected as a new AE in [PERSEPT 2](#).

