Primary Objective(s): 
To assess the efficacy of LR769 to prevent excessive bleeding and to achieve hemostasis in hemophilia A or B patients with inhibitors to factor VIII (FVIII) or factor IX (FIX) undergoing elective surgical or other invasive procedures.
Secondary Objective: 
To assess the safety of LR769 including the immunogenic potential of the drug product.
Study Design: 
This is an international, multicenter, single-arm, Phase 3 study. Patients aged 6 months to 75 years, inclusive, who have congenital hemophilia A or B with inhibitors and who are scheduled for an elective surgical or other invasive procedure will be enrolled. Different age restrictions may apply per local regulation and ethical considerations; enrollment of children <12 years of age will not begin until after review of data from the PERSEPT 2 study by the DMC.
 
After obtaining Informed Consent from the patient and/or the patient's parent(s)/legal guardian(s), patients who are scheduled for an elective surgical or other invasive procedure will have screening assessments performed to determine eligibility.
 
Patients who are or were participating in another LR769 study (eg, PERSEPT 2) and who meet all eligibility criteria will be allowed in this study if the study is open for enrollment in that age group.
 
Safety follow up will continue until 28 (± 3) days after the last dose of LR769.

Intraoperative Efficacy Assessments

Immediately after completion of the procedure, the surgeon or practitioner performing the procedure will assess the intraoperative efficacy of LR769. The patient's intraoperative response to treatment with LR769 will be assessed by the surgeon/practitioner and recorded as "excellent," "good," "moderate," or "poor."

Postoperative Efficacy Assessments

Efficacy assessments will be completed every 24 (\pm 2) hours and at last administration of LR769. The patient's postoperative response to treatment with LR769 will be assessed by the investigator or designee and recorded as "excellent," "good," "moderate," or "poor." If the patient is discharged while on treatment, these assessments will be done via telephone. The final assessment (which represents the primary efficacy outcome) will be performed by the investigator at the study center 48 (\pm 4) hours after last dose of LR769 and will be based upon the totality of assessments performed on the patient at each timepoint.

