- Analysis (including relationship to LR769, severity, and outcome) of AEs/SAEs between first LR769 administration and 28 (± 3) days after last administration of LR769
- Analysis of treatment-emergent thromboembolic events between start of procedure and 28 (± 3) days after last administration of LR769
- Analysis of allergic and anaphylactic reactions between start of procedure and 28 (± 3) days after last administration of LR769
- Analysis of treatment-emergent antibodies against LR769 or host-related impurities between start of procedure and 28 (± 3) days after last administration of LR769

All AEs will be coded using the Medical Dictionary of Regulatory Activities (MedDRA). The number and percentage of patients with any treatment-emergent AEs (TEAEs) and any treatment-emergent serious AEs (SAEs) will be presented for all patients. The number and percentage of patients with any treatment-emergent thromboembolic event and/or allergic and anaphylactic reactions will be presented for all patients.

For vital signs and clinical laboratory test results, descriptive statistics for the actual value at each timepoint and the change from baseline to each post baseline timepoint will be tabulated. Descriptive statistics for immunogenicity data will also be produced for the specified timepoints. Two-sided paired t-tests will be used to test whether the mean changes from baseline equal 0. Baseline is defined as the last measurement prior to study treatment.

Data Monitoring Committee

The Data Monitoring Committee (DMC) is responsible for the oversight of patient safety. The DMC will consist of 3 specialists in the care of hemophilia patients. DMC members will be independent of the study and Sponsor. During the course of the study, the DMC will review immediate serious adverse drug reactions and quarterly review of SAE listings. In addition the DMC will review the data and recommendation from the DMC in the [PERSEPT 2](#) pediatric study to determine when enrollment of patients <12 years of age is appropriate for this study.

Date of Original Approved Protocol: 02 September 2015

Date of Protocol Amendment 2: 18 February 2016

Date of Protocol Amendment 3: 03 August 2016

Date of Protocol Amendment 4: 20 December 2016

Date of Most Recent Protocol Amendment (if applicable): Not applicable

Prepared in: Microsoft Word 2010

TABLE OF CONTENTS

SYNOPSIS.....	2
LIST OF IN-TEXT TABLES.....	17
LIST OF APPENDICES.....	17

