6.9 Adverse Events Assessments

6.9.1 Performing Adverse Events Assessments

An AE is defined as any undesirable physical, psychological, or behavioral effect experienced by a patient or subject during their participation in an investigational study, in conjunction with the use of a drug or biologic, whether or not product related. Events that match this description but occur between the time of Informed Consent and the first administration of LR769 are also regarded as AEs, but will be listed as *non*-TEAEs. Disease signs, symptoms, and/or laboratory abnormalities already existing prior to Informed Consent are not considered AEs, unless they recur after the patient has recovered from the pre-existing condition or they represent an exacerbation in severity, duration, or frequency.

All AEs will be recorded in the patient's source record and on the eCRFs. A description of the event (preferably medical diagnosis, or if no diagnosis is made, symptom or sign) including start date/time, resolution date/time, seriousness, severity, relationship to LR769, action taken, and outcome will be provided.

All AEs will be followed up until resolution or 30 days after the last dose or early termination, whichever comes first.

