6.13 Removal of Patients from the Trial or Treatment

The investigator may withdraw a patient from the study for any of the following reasons:

- The investigator believes it is in the best interest of the patient to discontinue the study
- The Sponsor or investigator terminates the study
- The patient withdraws consent or requests to be discontinued from the study
- The patient is non-compliant

In case of early withdrawal of the patient, he will be asked to perform the 48 (\pm 4) hour visit assessment after last administration of LR769, unless he has withdrawn Informed Consent.

The investigator may discontinue a patient from LR769 treatment for any of the following reasons:

- AE or SAE possibly related to LR769 treatment
- A clinically significant change in the patient's condition that does not allow safe administration of LR769
- Per judgment of the investigator, if an adequate hemostatic response is not achieved with LR769, and the bleeding requires continued treatment, the treating physician should stop treatment with LR769 and treat the patient with a rescue therapy, such as another bypassing agent (e.g., FEIBA® or NovoSeven®) and/or other effective hemostatic treatment. The patient remains eligible for treatment with LR769 for a new surgical procedure taking into account the pharmacodynamic half-life of the rescue therapy given.

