9.6 Safety Endpoints and Analysis

Safety endpoints include the following:

- Analysis (including relationship to LR769, severity, and outcome) of AEs/SAEs between first LR769 administration and 28 (\pm 3) days after last administration of LR769
- Analysis of treatment-emergent thromboembolic events between start of procedure and 28 (\pm 3) days after last administration of LR769

- Analysis of allergic and anaphylactic reactions between start of procedure and 28 (± 3) days after last administration of LR769
- Analysis of treatment-emergent antibodies against LR769 or host-related impurities between start of procedure and 28 (± 3) days after last administration of LR769

All AEs will be coded using the Medical Dictionary of Regulatory Activities (MedDRA). The number and percentage of patients with any treatment-emergent AEs (TEAEs) and any treatment-emergent serious AEs (SAEs) will be presented for all patients. An AE will be considered treatment related if it has a definite, probable, or possible relationship to the study treatment or if the relationship to the study treatment is missing. AEs will be summarized at the patient level by MedDRA system organ class (SOC) and preferred term (PT) using frequencies and percentages. AEs will also be tabulated at the event level by SOC, PT, and severity and by SOC, PT, and relationship to study treatment.

The number and percentage of patients with any treatment-emergent thromboembolic event and/or allergic and anaphylactic reactions will be presented for all patients.

For vital signs and clinical laboratory test results (continuous parameters), descriptive statistics for the actual value at each timepoint and the change from baseline to each post baseline timepoint will be tabulated. Two-sided paired t-tests will be used to test whether the mean changes from baseline equal 0. Baseline is defined as the last measurement prior to study treatment. Descriptive statistics for immunogenicity data will also be produced for the specified timepoints.

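### Adverse-event collection ends at early termination although the safety endpoints run to 28 (±3) days after the last dose, so dosed patients who leave early are not actively followed for the full window

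*Protocol*

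**What the plan says.** **Collection and follow-up rules.** Protocol 6.9.2 collects adverse events from consent "until resolution or 30 days after the last dose or early termination, whichever comes first". Protocol 6.9.1 sets the same limit on follow-up: "All AEs will be followed up until resolution or 30 days after the last dose or early termination, whichever comes first".

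**Patients who leave.** Protocol 6.13 states "In case of early withdrawal of the patient, he will be asked to perform the 48" (±4) hour assessment, unless consent is withdrawn. Protocol 7.5 and the Early Termination column of Appendix 1 give one set of assessments, including adverse events and an immunogenicity sample. Neither states a later contact for these patients.

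**Endpoint windows.** The Synopsis and Protocol 3.1 state without exception: "Safety follow up will continue until 28 (± 3) days after the last dose of LR769". SAP 3.1 also runs safety assessment to that point. Protocol 9.6 and SAP 5 define the first safety endpoint as covering "AEs/SAEs between first LR769 administration and 28 (± 3) days after last administration of LR769". The thromboembolic endpoint reads "Analysis of treatment-emergent thromboembolic events between start of procedure and 28 (± 3) days after last administration of LR769", and the endpoints for allergic or anaphylactic reactions and for antibodies end at the same time.

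**Analysis.** SAP 6 puts every patient with at least one dose in the Safety Population. SAP 7.8.2 reports numbers and percentages of patients and numbers of events. SAP 7.3 has no rule for safety follow-up that stops early.

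**The concern.** The collection rule is shorter than the window that the endpoints claim to cover. A site that follows 6.9.2, 6.13 and 7.5 to the letter will not seek the data that 9.6 needs from a dosed patient who leaves early. That patient still counts in the denominator. If he had no event of a given type before leaving, he adds nothing to the numerator, and the table does not separate him from a patient followed to day 28.

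The study is small (at least 12 procedures in at least 6 patients), and under Protocol 6.12 one confirmed thrombotic event stops it. A single event missed for want of a contact would therefore matter. The loss may also be informative: SAP 7.3 foresees withdrawal from the study within 2 days of the last dose because of an adverse event or by the investigator's decision, combined with rescue therapy. The SAP imputes a poor efficacy response in that case and has no counterpart for safety.

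**Working it through.** The plan states no dropout rate, power or safety precision, so it has no figure of its own to reproduce. The check compares the windows and then sizes the gap.

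**Inputs from the documents**
- Endpoint window: 28 ± 3, that is days 25 to 31 after the last dose (Protocol 9.6).
- Collection limit: the earliest of resolution, day 30 or early termination (Protocol 6.9.2).
- Last requested contact after early withdrawal: 48 ± 4 hours, that is 44 to 52 hours after the last dose (Protocol 6.13).
- Minimum size: 12 procedures (Protocol 3.3, SAP 4).

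**Assumption:** w = 0 to 3 of the 12 procedures end in early withdrawal, with the last contact at 48 hours.

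**1. The 30-day limit.** Day 30 is later than nominal day 28. The most it can cut off is 31 − 30 = 1 day. Since 6.9.2 asks at each visit about everything since the previous one, a visit on day 31 would probably still capture it.

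**2. The early-termination limit.** Unobserved post-dose time = 28 − 2 = 26 days, or 26/28 = 93%. Over the visit windows this ranges from 25 − 52/24 = 22.8 days to 31 − 44/24 = 29.2 days. The treatment period, which is observed, also lies inside the endpoint window. With the 5-day minimum for major procedures completed, the unobserved share of the whole window is 26/(5 + 28) = 26/33 = 79%.

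**3. Effect on the study.**
- Observed share of post-dose time = [(12 − w) × 28 + w × 2] / (12 × 28).
- Crude percentage expected if the true 28-day risk is p with a constant hazard = [(12 − w) × p + w × (1 − (1 − p)^(2/28))] / 12, shown for p = 10% (illustrative).
- Upper 95% Clopper-Pearson limit for zero events among n fully followed procedures = 1 − 0.025^(1/n), with n = 12 − w.
- Upper bound on the missed proportion, if every early leaver had an unseen event = w/12.

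| w | Observed post-dose time | Crude % when true risk is 10% | Upper limit, 0 events in 12 − w | w/12 |
|---|---|---|---|---|
| 0 | 336/336 = 100% | 10.0% | 26.5% | 0% |
| 1 | 310/336 = 92% | 9.2% | 28.5% | 8.3% |
| 2 | 284/336 = 85% | 8.5% | 30.8% | 16.7% |
| 3 | 258/336 = 77% | 7.7% | 33.6% | 25.0% |

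The plan specifies no confidence intervals for safety, so the limits only illustrate scale. Dropping early leavers from n overstates the loss, because they were observed through the procedure, dosing and 48 hours.

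**The case against.** Five points can be made for the plan.

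- **Stopping LR769 is not leaving the study.** Protocol 6.13 has two lists. "AE or SAE possibly related to LR769 treatment" and inadequate hemostasis are reasons to stop treatment, and nothing there says that such patients leave. They have a last dose, so the 28-day visit in 7.6.2 applies. This stands. A reader might infer that patients with adverse events or failed hemostasis are the ones whose follow-up is cut; 6.13 does not support that as a general statement. But early termination is not defined, and SAP 7.3 and 7.8.2 do foresee study withdrawal because of adverse events.
- **Late events can still reach the sponsor.** Protocol 6.9.8.2 requires every serious event to be reported within 24 hours of the investigator's first knowledge, with no early-termination cut-off. Section 6.9.9 puts confirmed thrombotic events and acute allergic reactions associated with LR769 on the same route even if not serious, and the stopping rule in 6.12 has no collection window. This stands. A reader might infer that an event after termination can never be collected, or can never trigger the stopping rule. The documents do not say so. These routes depend on the investigator hearing of the event; they are not a planned contact.
- **Early departures will be visible.** SAP 7.4 tabulates withdrawals with the primary reason, and SAP 7.1 lists all data. This largely stands, but the safety tables would still not show how many procedures had complete 28-day follow-up.
- **The 30-day limit is harmless.** This stands. Replacing it with the 28 (±3) day visit alone would even shorten collection for patients seen on days 25 to 29.
- **The size is assumed.** This stands. No withdrawal count is given.

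**Conclusion.** The concern holds as a gap in active ascertainment. Sections 6.9.1, 6.9.2, 6.13 and 7.5 request nothing from an early leaver after the 48-hour or termination visit. The general follow-up statements and all four safety endpoints cover every dosed patient to 28 (±3) days. These passages must be reconciled.

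For one patient last seen at 48 hours, about 26 of 28 post-dose days pass without a planned safety contact. For the study, the loss is 8%, 15% or 23% of planned post-dose time for 1, 2 or 3 such exits among 12 procedures, and nil for none. These figures rest on the assumed number of exits and on an exit at 48 hours; the attenuation figures also assume a constant hazard and withdrawal unrelated to risk.

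Two stronger readings go too far. That early leavers are declared event-free is an inference from an all-dosed denominator, crude percentages and no rule for unobserved time; it is not stated, and it concerns only those without an event of that type before leaving. That the safety counts are biased downward is a possibility that depends on somebody leaving early and then having an event that goes unreported; the documents do not establish it.

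**What to change.** 1. **Protocol 6.9.1 and 6.9.2:** delete the early-termination limb. Collect adverse events until the later of 30 days after the last dose or the 28 (±3) day visit, so that nobody's collection is shortened and day 31 is covered.
2. **Protocol 6.13 and 7.5:** state that stopping LR769 is not in itself withdrawal from the study. Request one adverse-event and thromboembolic contact at 28 (±3) days from every dosed patient who leaves early without withdrawing consent. Telephone is enough. It will not supply the 28-day antibody sample, so for a patient reached only by telephone the sample from the early-termination visit remains the last one.
3. **Safety tables:** footnote the number of procedures with complete 28-day follow-up. SAP 7.1 allows this to be added before database lock, even if the protocol can no longer be amended.

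The cost is protocol wording, one telephone contact per early-terminated patient and a table footnote. Dosing and treatment rules are not affected.

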4.3 Exclusion Criteria

Patients who meet any of the following criteria will be excluded from the study.

1. have any coagulation disorder other than hemophilia A or B
2. be immunosuppressed (ie, the patient should not be receiving systemic immunosuppressive medication; CD4 counts at screening should be $>200/\mu\text{l}$)
3. known intolerance to LR769 or any of its excipients
4. currently receiving ITI therapy
5. have a known allergy or hypersensitivity to rabbits
6. have platelet count $<100,000/\mu\text{L}$
7. have received an investigational drug within 30 days of the planned first LR769 administration, or is expected to receive such drug during participation in this study (with the exception of patients who are or were participating in another LR769 study, eg, a study assessing the treatment of bleeding episodes with LR769)
8. have a clinically relevant hepatic (aspartate aminotransferase [AST] and/or alanine aminotransferase [ALT] >3 times the ULN and/or renal impairment (creatinine >2 times the ULN)
9. have a history of arterial and/or venous thromboembolic events (such as myocardial infarction, ischemic strokes, transient ischemic attacks, DVT, or PE) within 2 years prior to the planned first dose of LR769, uncontrolled arrhythmia, or current New York Heart Association (NYHA) functional classification score of stages II – IV
10. have an active malignancy (those with non-melanoma skin cancer are allowed)
11. have any life-threatening disease or other disease or condition which, according to the investigator's judgment, could imply a potential hazard to the patient, or interfere with the trial participation or trial outcome (eg, a history of non-responsiveness to bypassing products)
12. be using aspirin, NSAIDS, herbs, natural medications, or other drugs with platelet inhibitory properties within one week prior to surgery and for the duration of treatment with LR769
13. have active gastric or duodenal ulcer disease

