7.8.2 Adverse Events

All AEs will be coded using MedDRA (Version 15.0). An AE will be considered a treatment-emergent adverse event (TEAE) if it occurred or worsened after the first dose of study drug. In case a patient undergoes multiple procedures in the study, the TEAE will be assigned to the latest procedure prior to the event itself. Non-TEAEs are AEs occurring after signing Informed Consent but before the first administration of study drug. TEAEs will be summarized for the Safety Population. Non-TEAEs will be summarized for all enrolled patients.

The number and percentage of patients as well as the number of events will be summarized for any TEAEs, any treatment emergent SAEs, any treatment-related TEAEs, any non-treatment-related TEAEs, any TEAEs leading to discontinuation from the study, any TEAEs leading to study drug withdrawal and any TEAEs resulting in death. Summaries will be done stratifying by SOC and PT. An AE will be considered treatment related if it has a definite, probable, or possible relationship to the study treatment or if the relationship to the study treatment is missing. Additionally, a summary of TEAE's by SOC, PT, and severity grade will be created.

Separate summaries and listings will be provided for treatment-emergent thromboembolic events and allergic and anaphylactic reactions.

A data listing of TEAEs will be produced. Separate listings will also be prepared for SAEs, AEs leading to death, TEAEs leading to discontinuation from the study, TEAEs

leading to study drug withdrawal, thromboembolic AEs, and allergic and anaphylactic AEs. A listing of deaths will be provided as well, including information about the primary reason for death.

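### Protocol 6.9.2 directs worsening or recurring adverse events to PERSEPT 2 once a patient rejoins it, and nothing ties rejoining to the 28-day visit, so such events can be missing from this trial's safety tables

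*Protocol*

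**What the plan says.** Protocol 6.9.2 sets three rules for patients shared with PERSEPT 2.

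- For an event arising in this trial while "the patient is still enrolled in PERSEPT 2, the AE should only be collected in PERSEPT 3".
- For an unresolved event: "If the AE is ongoing at the time of rejoining PERSEPT 2, that AE should be only collected in PERSEPT 2 under medical history".
- For a change after rejoining: if "there is an exacerbation or recurrence of the AE, this AE should be collected as a new AE in" PERSEPT 2.

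The same section collects adverse events in this trial "until resolution or 30 days after the last dose or early termination, whichever comes first"; 6.9.1 applies the same limit to their follow-up. Protocol 9.6 and SAP 5 define the safety endpoint as the analysis of "AEs/SAEs between first LR769 administration and 28" (±3) days after last administration. Under SAP 7.8.2 an event is treatment-emergent "if it occurred or worsened after the first dose of study drug", and Protocol 6.9.9 agrees.

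On overlap, exclusion criterion 7 (Protocol 4.3) bars other investigational drugs before and during participation, "with the exception of patients who are or were participating in another LR769 study". No section gives an earliest day for rejoining PERSEPT 2.

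**The concern.** The third rule assigns an event to the other trial by whether the patient has rejoined. The safety endpoint assigns it by days since last dose. The two agree only if rejoining never happens before the 28-day visit, and no one has written that down.

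A hypothetical case shows the effect. A patient has an event recorded here as mild, rejoins PERSEPT 2 on day 5 after last dose, and the event becomes severe on day 15. A site following 6.9.2 enters the severe event in PERSEPT 2. This trial's tables keep a mild event, although day 15 lies inside the endpoint window and the worsening meets the treatment-emergent definition.

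The patient still counts as having an adverse event. What can go missing is the higher severity, any new seriousness or change in relatedness, and the extra event in event-level counts. An event that began between consent and first dose is treatment-emergent only if it worsens. If it first worsens after rejoining, the treatment-emergent event could be missing altogether.

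Protocol 10.8 describes PERSEPT 2 as a pediatric study, and SAP 7.8 repeats safety summaries for patients under 12 and those 12 or older. Any effect may therefore concentrate in a small stratum.

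**Working it through.** The plan has no figure to reproduce here: SAP 4 bases the sample size on guidelines, without power or effect size. The check is a comparison of texts, followed by illustrative arithmetic.

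**1. Which rule covers an event that worsens after rejoining but before the 28-day visit?**

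| Source | What it implies |
|---|---|
| Protocol 6.9.2, rejoining rule | New event in PERSEPT 2; no matching instruction for this trial |
| Protocol 6.9.2, general rule | Collected here to resolution, 30 days or early termination |
| Protocol 9.6 and SAP 5 | Belongs to this trial's endpoint |
| Protocol 6.9.9 and SAP 7.8.2 | Treatment-emergent |
| Protocol 3.3 | Participation runs to the last follow-up visit; not linked to rejoining |

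No passage says which governs. For an event that resolved and then recurs, the general rule is weaker still, because it stops at resolution.

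**2. Does the SAP close the gap?** SAP 7.1 and 7.8.2 handle repeat procedures within this study by assigning an event to the latest preceding procedure. For other LR769 studies, SAP 7.4 only counts previously enrolled patients. There is no rule to retrieve PERSEPT 2 events or to censor at rejoining.

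**3. How much of the window is exposed?** The rejoining day r (days after last dose) is not in the documents, so a range is assumed. Days left = 28 − r; share = (28 − r)/28.

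| r | Days left of 28 | Share |
|---|---|---|
| 2 (at the 48-hour visit) | 26 | 93% |
| 7 | 21 | 75% |
| 14 | 14 | 50% |
| 21 | 7 | 25% |
| 25 | 3 | 11% |
| 28 | 0 | 0% |

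Against the 30-day collection rule, r = 28 leaves 30 − 28 = 2 days. A visit on day 25, which the ±3 allows, followed at once by rejoining leaves 30 − 25 = 5 days.

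**4. What is one event worth?** The minimum size is 12 procedures in 6 patients (Protocol 3.3, SAP 4). Suppose the moved event is the only one in its category, such as the only severe event. The Clopper-Pearson 95% intervals are added for illustration; the plan does not promise them for adverse events. For x = 0 the upper limit is 1 − 0.025^(1/n). For x = 1 the lower limit is 1 − 0.975^(1/n) and the upper is the 97.5% quantile of Beta(2, n − 1).

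| Unit | Event kept | Event moved out |
|---|---|---|
| Procedures | 1/12 = 8.3% (0.2% to 38.5%) | 0/12 (0% to 26.5%) |
| Patients | 1/6 = 16.7% (0.4% to 64.1%) | 0/6 (0% to 45.9%) |

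The number of rejoining patients and their event rate are not given, so an expected loss cannot be computed.

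**5. LR769 given under PERSEPT 2 before the 28-day visit.** Protocol 5.5 and 6.11 already require such a dose to be recorded as concomitant therapy. SAP 7.9.2, however, counts a drug as concomitant only if it started in the treatment period, or started before the first treatment and ended within that period. A later dose would not be summarized, although the general promise in SAP 7.1 to list all collected data would still cover it. Nothing in either document limits *last dose of LR769* to doses given under PERSEPT 3.

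**The case against.** The strongest reply is that rejoining naturally means returning after this trial's follow-up has ended. Participation runs to the last follow-up visit, and re-entry is presumably governed in part by the PERSEPT 2 protocol, which is not available here. On that reading the rule is an ordinary hand-over that avoids double counting and leaves the 28-day endpoint intact. This is plausible, but the text does not say it, and both exclusion criterion 7 and the words on patients still enrolled in PERSEPT 2 allow overlap.

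Second, the sentence on worsening lacks the word *only*, which the two sentences before it contain. The general rule still runs to 30 days, and the 28-day visit (Protocol 7.6.2) asks about adverse events and thromboembolic signs again. Entry in both trials is therefore a possible reading. This stands, and it makes the matter an unresolved conflict. A site reading the paragraph as a whole would still tend to enter each event once.

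Third, serious events go to the sponsor within 24 hours (Protocol 6.9.8.2), and allergic reactions and confirmed thrombotic events associated with LR769 follow the same route (6.9.9). This also stands: the weakness lies in this trial's tables, not in urgent safety reporting.

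A reader might infer more: that events are certainly lost, that exposure from the two trials is mixed, or that the day-28 antibody result cannot be attributed to the surgical course. The documents support none of these. Loss needs rejoining inside the window, which is neither stated nor excluded. No passage puts PERSEPT 2 doses into this trial's exposure tables. Antibody samples are also taken before the procedure, at 7-14 days and 48 hours after last dose, so a later PERSEPT 2 dose would complicate the day-28 result without making the series uninterpretable.

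**Conclusion.** The point holds as a conflict between a stated recording rule and the endpoint window. If a patient rejoins PERSEPT 2 before the 28 (±3)-day visit, following 6.9.2 as written can leave worsened or recurrent events out of this trial's safety tables, and the SAP has no means of bringing them back. Only events already recorded in PERSEPT 3 are affected.

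The 26-day exposure is a worst case that assumes rejoining at the 48-hour visit. The 8.3% and 16.7% figures are what any single event weighs at minimum size; they do not estimate a loss. The number of patients concerned is unknown and may be zero. The passages should be reconciled because the safety data set is small enough for one misplaced event to matter and the correction is cheap.

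**What to change.** - **Protocol 6.9.2 and SAP 7.8.2:** state that every adverse event with onset, worsening or recurrence up to the 28 (±3)-day visit is recorded and analysed in PERSEPT 3, whether or not the patient has rejoined PERSEPT 2. Cross-flag it if it is also entered there.
- **Follow-up clock:** define the last dose of LR769 as the last dose given under PERSEPT 3.
- **SAP:** flag the day-28 safety and antibody results of any patient who received LR769 under PERSEPT 2 before that visit, since SAP 7.9.2 would not summarize a dose given after the treatment period.

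If rejoining in practice always follows the 28-day visit, one sentence saying so would remove most of the conflict, leaving only the few days between that visit and the 30-day collection limit.

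The cost is wording in two documents, a cross-study flag and some double entry across the two databases. No extra visits and no change to treatment access are needed.
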